#### 13.5 Secondary Analyses

1. Proportion of patients alive AND free of ventilator use / ECMO at Day 28: The proportion will be evaluated based on the number of patients who are alive AND free of

ventilator use or ECMO at Day 28 after study entry divided by the number of total patients enrolled for each treatment arm. The proportion of patients who have this event will be analyzed similarly to the primary endpoint. Comparisons will be done by use of independent samples Z-test for proportions and a 95% confidence interval will be constructed for the difference between groups. The Cochran-Mantel-Haenszel test will be used to include stratification factors. Multivariable logistic regression models will be used to assess the influence of treatment arm on while adjusting for other factors of interest.

**2. Time to death and Mortality rate:** The Kaplan-Meier method will be used evaluate differences in the distributions of time-to-death between treatment arms. Rates of mortality at day 28 and day 56 mortality will be estimated. Patients lost to follow-up or who withdraw early will be considered censored at their last assessment date for the Day 28 rate. The stratified log-rank test will be used to compare differences in distributions of time to death based on stratification factors. Cox proportional hazards model will be used to compare treatment arms with inclusion of stratification factors or adjustment for covariates of interest.

**3. Time to clinical improvement:** Time to clinical improvement will be evaluated using Kaplan-Meier methods and Cox regression models. Rates of clinical improvement at days 14 and 28 will be estimated. Time to clinical improvement will be assessed after all patients have reached day 14 and 28; no clinical improvement at day 14 or 28 or death before day 14 or 28 will be considered as right censored. Hazard ratios with 95% confidence intervals will be calculated by the Cox proportional-hazards model. Covariates of interest will be included in regression models.

**4. Clinical status at Days 14 and 28:** The distribution of the clinical status will be summarized by arm at days 14 and 28. A proportional odds model with treatment arm and disease severity at baseline as covariates will be used to evaluate whether the odds of improvement on the ordinal scale are higher for the treatment arm as compared to control.

**5. Length of Stay:** Length of stay will be defined as the time from study entry until the time of hospital discharge and the number of days hospitalized will be compared between groups by use of non-parametric Wilcoxon rank-sum test. The proportions of patients who require an ICU admission will be compared between randomized groups by the use of independent samples Z-test for proportions and a 95% confidence interval will be constructed for the difference between groups. In addition, time in the ICU will be described in number of days spent receiving ICU care, if applicable.

**6. Duration of Mechanical ventilation / ECMO:** Duration of ventilator / ECMO use will be summarized by medians or quartiles by arm for those subjects who have a baseline score of 6-7 at study entry.

**7. Duration of non-invasive ventilation / high-flow oxygen:** Duration of non-invasive ventilation / high-flow oxygen will be summarized by medians and quartiles by arm for those patients who have a clinical status score of 5 at study entry.

**8. Duration of supplemental oxygen use:** Duration of supplemental oxygenation use will be summarized by medians and quartiles by arm for those patients who have a clinical status score greater than or equal to 4 at study entry.

**9. Occurrence of adverse events related to treatment:** Analyses for safety will include all participants who are randomized and received at least 1 dose of study treatment.

Participants will be grouped according to the treatment to which they were randomized. Events will be summarized on the basis of the date of onset for the event. The maximum grade for each type of adverse event will be recorded for each patient. Frequency tables of adverse events will be constructed based on maximum grade for each treatment arm. Overall adverse event rates, rates of grade 3 or higher events and serious adverse events will be compared between treatment groups using Chi-square or Fisher's exact test.

**10. Development of thrombosis / bleeding complications:** Incidence of arterial and venous thrombosis or bleeding complications will be described and compared by treatment arms by use of chi-square or Fisher's exact test.

Subgroup analyses for the primary and secondary analyses will examine the treatment effect across the following subgroups of interest. Forest plots with odds ratio and 95% confidence intervals will be presented along with interaction tests.

- Duration of symptoms prior to enrollment: <= Median versus > Median number of days,
- Comorbidities, presence of Hypertension/CHF/COPD/coronary artery disease: Yes versus No,
- Age: <65 versus >= 65 years,
- Sex: Female versus Male,
- Baseline severity of disease: Mild/moderate versus Severe disease

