## 5.0 Stratification Factors

- 5.1 Age:  $\geq 65$  vs.  $< 65$  years
- 5.2 Clinical status ordinal score at enrollment: 3-4 (hospitalized with mild disease) vs. Score 5 (hospitalized with severe disease)

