## 12.0 Treatment Evaluation Criteria

The ordinal scale used for assessment of the clinical and respiratory status on each day of the study is included below. Each day, the worst (i.e., highest ordinal) score from the previous day will be recorded, i.e., on Day 3, the highest ordinal score from Day 2 is obtained and recorded for Day 2. The scale is as defined by the WHO as follows:

Patient State	Descriptor	Score
Uninfected	No Clinical or Virological Evidence of Infection	0
Ambulatory	No Limitation of activities	1
	Limitation of activities	2
Hospitalized, Mild Disease	Hospitalized, no oxygen therapy	3
	Oxygen by mask or nasal prongs	4
Hospitalized, Severe Disease	Non-invasive ventilation or high flow oxygen	5
	Intubation and Mechanical Ventilation	6
	Ventilation + additional organ support-pressors, RRT, ECMO	7
Dead	Death	8

In addition, patients will be stratified at baseline based on the ordinal scale below. A score of 3-4 is associated with hospitalized with mild disease versus score of 5 is associated with severe disease.

The primary outcome assessment for efficacy will be evaluated based on the number of patients who are alive AND respiratory failure-free at Day 28 after study entry.

Respiratory failure at Day 28 will be defined by clinical diagnosis of respiratory failure corresponding to a score of 5-8 on the above ordinal scale at Day 28. Specifically, respiratory failure is defined by meeting any of the following criteria:

- Requiring ICU admission,
- mechanical ventilation,
- ECMO,
- non-invasive ventilation,
- or high flow oxygen devices,

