## 13.0 Statistical Considerations and Methodology

### 13.1 Statistical Design

The study design will be a randomized (1:1 ratio), double-blinded, placebo-controlled phase II trial of 264 patients. Randomization will be stratified based on age (< 65 years versus  $\geq$  65 years) and disease severity at study entry (hospitalized with mild disease versus hospitalized with moderate/severe disease). The purpose of this study is to evaluate the efficacy of Camostat mesilate in addition to SOC treatment as compared to SOC treatment combined with placebo with respect to clinical status on Day 28. The proportion of patients alive AND free from respiratory failure at Day 28 will be the primary outcome.

Patients will be analyzed according to their randomization assignment. All patients meeting eligibility criteria who received at least 1 dose of study drug will be included in the analysis.

Formal interim analysis will be conducted after the first 66 patients (33 treated in the treatment arm and 33 in the control group) have completed the 28 Day assessment period. Safety analyses will be done to assess occurrence of any differences in adverse events between the treatment arms. A second interim analysis will occur after 132 patients (66 in the treatment arm and 66 in the control group) have completed the 28 Day assessment period.

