#### 13.4 Planned Analyses

##### Primary Analysis

Frequency distributions and chi-square tests will be used to screen for major imbalances in the two randomization groups for qualitative variables; graphical displays including box plots and summary statistics (e.g., mean, median, standard deviation, ranges, etc.) will be used for quantitative variables with t-tests (after appropriate transformations if necessary to meet the assumptions of the methods).

The primary outcome will include the number of patients who are alive AND free from respiratory failure at Day 28 divided by the total number of patients in each arm. This endpoint will be analyzed in a binary fashion using properties of the binomial distribution and will be compared between randomized arms by the use of independent samples Z-test for proportions and a 95% confidence interval will be constructed for the difference between arms. Proportions will also be compared using Cochran-Mantel-Haenszel tests, including the stratification factors of age and baseline disease severity. Multivariable logistic regression models will be used to assess the influence of treatment while controlling for covariates of interest (gender, symptom onset, comorbidities) along with stratification factors. Primary analysis for this efficacy outcome will include all participants who are randomized and received at least 1 dose of study treatment. Participants will be analyzed according to the treatment to which they were randomized.

Efforts to minimize loss to-follow-up will be considerable. However, small amounts of missing data may occur. In such cases, participants without Day 28 outcome data will be excluded from the analysis. Sensitivity analyses will evaluate the impact of making different assumptions about the missing observations.

**Interim analyses:** Two interim analyses will be conducted after 25% and 50% of patients have completed the 28 day study period. The interim analysis will include the below stopping rules for efficacy and futility based on a Lan-DeMets spending function with O'Brien-Fleming boundaries. Occurrence of adverse events will also be evaluated at the interim analysis.

Accrual	Control arm (#)	Camostat arm (#)	Total number (#)	Efficacy boundary (Z scale)	Alpha spent	Futility boundary (Z scale)	Beta spent
25%	33	33	66	+/- 4.33	0.001	+/- 0.007	0.002
50%	66	66	132	+/- 2.96	0.003	+/- 0.34	0.04
100%	132	132	264	+/- 1.97	0.05	+/- 1.97	0.20

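### The Day 14/28 proportional odds model should name the baseline ordinal score as its severity covariate; the documents define severity only as two levels, and not consistently

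*Combined protocol and SAP*

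**What the plan says.** Section 13.5 item 4 specifies for the ordinal outcome: "A proportional odds model with treatment arm and disease severity at baseline as covariates will be used". No coding of severity follows.

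Elsewhere, baseline severity always has two levels:

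- Section 5.2: "Clinical status ordinal score at enrollment: 3-4 (hospitalized with mild disease) vs. Score 5 (hospitalized with severe disease".
- Section 12.0: "A score of 3-4 is associated with hospitalized with mild disease versus score of 5 is associated with severe disease".
- Section 13.1: "disease severity at study entry (hospitalized with mild disease versus hospitalized with moderate/severe disease".
- Subgroup list at the end of Section 13.5: "Baseline severity of disease: Mild/moderate versus Severe disease".

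The supportive logistic model for the primary endpoint (Section 13.4) assesses treatment while "controlling for covariates of interest (gender, symptom onset, comorbidities) along with stratification factors", so there the two-level factor is explicit. The primary endpoint itself "will be compared between randomized arms by the use of independent samples Z-test for proportions", without covariates.

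The Section 4.0 schedule marks the ordinal scale assessment at baseline. Eligibility (3.1.6) asks for a score of at least 3 and states no upper limit. Sections 13.3.2 and 13.5 define ventilator/ECMO days for patients whose baseline score is 6-7.

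**The concern.** The outcome in item 4 is the ordinal score at Day 14 or 28, and its baseline value is known for each patient. If severity is entered as two levels, patients without oxygen (3) and with oxygen (4) are treated as alike, and so are score 5 and any enrolled 6-7. The plan itself separates these groups elsewhere: oxygen days are counted only from baseline 4 upward, non-invasive ventilation days only from baseline 5, and ventilator days only from baseline 6-7. Dropping that information costs some power in a secondary analysis, and nothing has to be collected to recover it.

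The definition is also unsettled. The scale has no 'moderate' category, yet 13.1 groups 'moderate' with severe and the subgroup list groups it with mild. A patient entering at 6 or 7 meets the eligibility wording but has no level in the factor of 5.2 and 12.0. An analyst could not code that patient from the documents.

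**Working it through.** **1. The plan's own figure.** The only stated power is for the primary Z-test: 132 per arm, 80% vs 92%, two-sided 0.05, unpooled variance (Section 13.6).

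- n = [0.80×0.20 + 0.92×0.08] × (1.960 + 0.842)² / 0.12² = 0.2336 × 7.849 / 0.0144 = 127.3, so 128 per arm. The pooled formula gives 131.
- Power at 132 per arm: 0.12 / √(0.2336/132) − 1.96 = 0.893, or 81.4% (80.6% pooled).

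The stated 80% is reproduced to within 2 points. No covariate enters this calculation, so severity coding cannot change it. The documents give no power figure for the proportional odds model.

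**2. Simulation of the item 4 model.** Taken from the plan: 264 patients, 1:1, treatment plus baseline severity as covariates. Assumed, because the documents do not give them:

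- a control Day 28 distribution with 20% in scores 5-8;
- a treatment odds ratio of 2 (log 0.693);
- an effect of 0.5, 1.0 or 1.5 on the log-odds scale per baseline point;
- the baseline mixes in the table.

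Both codings were fitted to the same simulated data. Relative efficiency = (mean z with categorical score / mean z with 3-4 vs 5 or higher)². Power (%), two-level → score, is in brackets.

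| Baseline mix (%) | 0.5 per point | 1.0 per point | 1.5 per point |
|---|---|---|---|
| 3/4/5: 10/60/30 | 1.011 (86.0→86.0) | 1.031 (86.2→87.0) | 1.049 (86.0→86.0) |
| 3/4/5: 30/40/30 | 1.011 (85.8→85.8) | 1.051 (88.0→88.5) | 1.116 (82.0→85.5) |
| 3/4/5: 40/40/20 | 1.016 (86.8→87.0) | 1.071 (79.5→83.0) | 1.132 (82.0→86.0) |
| 3-7: 10/55/25/7/3 | 1.020 (84.3→85.6) | 1.077 (86.6→89.5) | 1.176 (77.4→84.6) |
| 3-7: 20/40/20/15/5 | 1.042 (86.5→88.8) | 1.115 (82.6→85.8) | 1.235 (80.3→87.5) |

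Each cell had 400 runs, and runs in which a fit failed were dropped. All 400 were usable with scores 3-5. In the two bottom-right cells only 208 and 279 were, so those figures are the least secure. A score level holding 3% of 264 has about 8 patients, which is why sparse levels need a merging rule. The Monte Carlo standard error of one power value near 85% is √(0.85×0.15/400) = 1.8 points.

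**3. Where the gain comes from.** Take mix 30/40/30 at 1.5 per point. The mean log odds ratio moves from −0.653 to −0.697 (truth −0.693), while the mean standard error goes from 0.228 to 0.230. The estimate is less attenuated; its standard error does not fall.

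**4. Second simulation, different assumptions.** Baseline 3/4/5/6-7 at 20/45/25/10%, treatment log odds ratio −0.65, age group in both models, 2,000 trials. Power rose from 77.5% to 78.3% (moderate prognostic strength) and from 73.4% to 75.9% (strong). Equivalent sample size, ((1.96 + z₂)/(1.96 + z₁))²:

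- moderate: ((1.96 + 0.782)/(1.96 + 0.755))² = 1.020;
- strong: ((1.96 + 0.703)/(1.96 + 0.625))² = 1.061.

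Simulated type I error was at most 0.057 under either coding, against a Monte Carlo standard error of √(0.05×0.95/2000) = 0.005. A further paired simulation gave 1-8%, with no visible rise in type I error.

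**5. Linear or categorical.** A single linear score performed like the categorical score throughout (for 30/40/30 at 1.5, both had 85.5% power). The score effect was simulated as linear in step 2, so this is partly by construction.

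**6. Room in the logistic model.** Expected failures: 132×0.20 + 132×0.08 = 37. The planned model has at least six terms (treatment, age, severity, gender, symptom onset, comorbidities): 37/6 = 6.2 failures per term. Two extra severity levels would give 37/8 = 4.6. A linear score in place of the two-level factor stays at six terms.

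**The case against.** The strongest reply is that item 4 never says two levels. Where the plan means the stratification factors it says so, as in 13.4; item 4 uses a different phrase, and entering the score would already comply. That stands. A reader might infer that the plan fixes a two-level covariate in item 4, but the text leaves it open. The case for change is therefore partly a case for stating the coding.

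Other stronger readings are also unsupported:

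- **Precision is lost.** In this model the standard error does not shrink with the finer score. What is lost is some power, and the conditional odds ratio being estimated shifts slightly.
- **The treatment estimate is biased.** Minimisation does not balance 3 against 4 within a stratum, but any remaining imbalance is chance.
- **The Cox model for death must change too.** Section 13.5 item 2 offers stratification factors or covariate adjustment as alternatives, and no calculation here supports a change.
- **Age should be entered in years.** No result here isolates a gain from that.
- **The primary conclusion is at risk.** The primary test is unadjusted.

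It is also fair that the gain is small and driven by assumptions. In the moderate case of the second simulation, the 0.8-point rise is within the Monte Carlo standard error of a single power estimate, √(0.775×0.225/2000) = 0.93 points. Adjusting for a factor as randomised is a defensible default. The remaining argument is that the score is already collected and costs at most a few parameters.

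**Conclusion.** The point holds as a modest improvement to a secondary analysis, together with a definition that needs repair. Using the baseline score in item 4 is worth about 1-8% in effective sample size under moderate to strong prognostic assumptions. Across the table the range is 1-13% for scores 3-5, with power gains of 0 to 4 points, and 2-24% when 10-20% of patients enter at 6-7. The baseline mix and prognostic strength behind all of these figures are assumed. No simulated scenario favoured the two-level factor on efficiency, and type I error was not visibly raised.

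The labelling defect rests on the text alone: 'moderate' changes sides between 13.1 and the subgroup list, and scores 6-7 are admitted by 3.1.6 and analysed in 13.3.2 and 13.5 without a level in 5.2 or 12.0. Using the score as a covariate does not cure this, because the two-level factor remains in the randomisation, the Cochran-Mantel-Haenszel test, the stratified log-rank test and the subgroups.

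**What to change.** 1. **Section 13.5 item 4:** state that the covariate is the baseline ordinal score, entered as a single linear term or as categories, with the rule for merging sparse levels written down before unblinding.
2. **Section 13.4 logistic model:** a single linear score term may replace the two-level factor, at no extra parameter.
3. **Sections 5.2, 12.0, 13.1 and the subgroup list:** use one definition of the severity factor. Remove 'moderate' or define it, reconcile the factor with 3.1.6 and the baseline 6-7 analyses so that every eligible score has a level, and record how any such patients already randomised were classified.

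Leave the primary Z-test, the Cochran-Mantel-Haenszel and stratified log-rank tests, the Cox model and the coding of age as planned. The cost is wording: no new data, at most a few parameters in item 4, and a slightly different conditional odds ratio to report.

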#### 6.1.8 Kits are available on site.

### 6.2 Randomization Procedures

6.2.1 The factors defined in Section 5.0, together with the registering membership (site of institution) will be used as stratification factors.

6.2.2 After the patient has been registered into the study, the values of the stratification factors will be recorded, and the patient will be assigned to one of the following treatment groups using the Pocock and Simon dynamic allocation procedure which balances the marginal distributions of the stratification factors between the treatment groups.

All patients must be registered before starting therapy. Under no circumstances will non-registered patients be retrospectively eligible for the study.

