### 13.6 Sample Size

Randomization will be done according to a 1:1 ratio. Based on data from Wang et al, 82% of patients treated with Remdesivir were alive and free from respiratory failure at day 28. In the preliminary report of Remdesivir for the treatment of COVID-19 in 1059 hospitalized patients, approximately 70% of patients treated with Remdesivir were alive and free from respiratory failure at Day 15; Day 28 data are not yet available. Using an expected proportion of 80% for the SOC control arm, this study would require 132 patients in each arm (total of 264 patients). Sample sizes of 132 in each arm achieves 80% power to detect a difference between the group proportions of 12% for the primary endpoint. The proportion in the treatment arm is assumed to be 80% under the null hypothesis and 92% under the alternative hypothesis. The proportion in the SOC arm is 80%. The test statistic used is the two-sided Z-Test with unpooled variance. The significance level of the test is 0.05 (two-sided).

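### The ordinal clinical-status model leaves out age, a stratification factor; if age is prognostic this costs some power, and adding it costs nothing measurable

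*Combined protocol and SAP*

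**What the plan says.** Section 13.5 item 4 compares the arms on the WHO ordinal scale at Days 14 and 28 with "A proportional odds model with treatment arm and disease severity at baseline as covariates". The list of covariates reads as complete, and no reason is given for leaving age out.

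Age is a design factor. Section 5.0 lists it with baseline clinical status, and Section 13.1 repeats this: "Randomization will be stratified based on age" and disease severity. Section 6.2 adds a third factor, since the Section 5.0 factors "together with the registering membership (site of institution) will be used as stratification factors". Allocation uses the "Pocock and Simon dynamic allocation procedure which balances the marginal distributions of the stratification factors between the treatment groups".

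Other analyses do use age. Section 13.4 compares the primary proportions with "Cochran-Mantel-Haenszel tests, including the stratification factors of age and baseline disease severity", and its logistic model carries the stratification factors too. Item 1 of Section 13.5 repeats that approach for the ventilator- and ECMO-free proportion. For time to death, item 2 says: "The stratified log-rank test will be used to compare differences in distributions of time to death based on stratification factors".

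Nothing elsewhere adds age to item 4. The sentence on including covariates of interest in regression models belongs to item 3, time to clinical improvement. The list of subgroups at the end of Section 13.5 includes age, but a subgroup analysis does not adjust the main comparison.

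**The concern.** When allocation forces balance on a prognostic factor, the treatment estimate varies less from trial to trial than it would under simple randomisation. A model that omits the factor does not know this. Its standard error is then larger than the true sampling SD, and the test rejects too rarely under the null.

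The odds ratio is also non-collapsible. With age left out, the model estimates an odds ratio averaged over age, which lies closer to 1 than the odds ratio within age groups. The two effects together reduce power.

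At stake is some efficiency in one secondary comparison, along with its consistency with the plan's own age-adjusted analyses. Age group is already recorded for every patient before allocation.

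**Working it through.** **The plan's own figure.** The documents give no power or effect size for the ordinal model. The only stated figure is for the primary endpoint: "Sample sizes of 132 in each arm achieves 80% power to detect a difference between the group proportions of 12% for the primary endpoint" (80% vs 92%, two-sided 0.05, unpooled Z-test).

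- n per arm = (1.960 + 0.842)² × (0.80×0.20 + 0.92×0.08) / 0.12² = 127.3, so 128.
- At 132 per arm the standard error is √(0.2336/132) = 0.0421, and power = Φ(0.12/0.0421 − 1.960) = 0.814.

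The stated 80% is reproduced to within 2 points. This supplies N = 264 and alpha for what follows.

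**Simulation of item 4.**

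- From the documents: N = 264, 1:1 allocation, Pocock-Simon minimisation, two-sided 0.05.
- Assumed, because the documents do not give them: biased-coin probability 0.8, 45% aged ≥65, 30% severe, severity odds ratio 4, six outcome categories with 80% of controls at score 4 or below, treatment odds ratio 0.50 for a worse score.
- The age odds ratio is varied from 1 to 5. Minimisation is on age and severity.
- Each of 5000 trials per setting is fitted with and without age. Monte Carlo error is about 0.3 points for type I error (√(0.05×0.95/5000)) and 0.5 points for power.

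| Age OR | Type I error, age omitted | Type I error, age included | Power, age omitted | Power, age included | Power loss (points) |
|---|---|---|---|---|---|
| 1 | 5.3% | 5.4% | 83.1% | 83.2% | 0.1 |
| 1.5 | 4.7% | 4.8% | 84.4% | 84.7% | 0.3 |
| 2 | 4.8% | 5.2% | 82.8% | 83.9% | 1.1 |
| 3 | 4.1% | 5.0% | 80.6% | 83.3% | 2.7 |
| 5 | 3.5% | 5.0% | 77.7% | 83.5% | 5.8 |

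**Where the conservatism comes from.** Under the null with age omitted, the mean model standard error and the true SD are 0.2263 and 0.2190 at age OR 3, and 0.2261 and 0.2103 at age OR 5. The effective critical value is 1.96 × SE/SD:

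- OR 3: 1.96 × 1.033 = 2.025, which implies a type I error of 4.3% (simulated 4.1%).
- OR 5: 1.96 × 1.075 = 2.107, which implies 3.5% (simulated 3.5%).

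**Where the power comes from.** Under the alternative, take |log OR| / mean standard error:

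- OR 3, age omitted: |ln 0.520| / 0.2356 = 2.78. Age included: |ln 0.497| / 0.2399 = 2.91.
- OR 5, age omitted: |ln 0.537| / 0.2346 = 2.65. Age included: |ln 0.491| / 0.2432 = 2.92.

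The reported standard error rises when age is added. The ratio improves because the conditional odds ratio is further from 1.

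**With site also in the minimisation.** Results at age log odds ratios 0.5, 1.0 and 1.5 (odds ratios 1.65, 2.72 and 4.48):

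- 2400 trials per setting: power without vs with age is 83.1% vs 83.9%, 80.6% vs 83.5%, and 77.0% vs 82.8%. The losses are 0.8, 2.9 and 5.8 points.
- A separate run of 4800 trials per setting, with four sites assumed: losses of 0.8, 3.0 and 6.7 points, and type I error without age of about 3.5% at the largest age effect.

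**The case against.** The strongest objection is that the loss is conditional. A reader might infer that the test is conservative and loses power as a matter of course. The documents do not support that, because they give no age effect. Up to an age odds ratio of 2 the loss is about 1 point or less, and type I error is close to 5%. Choosing age as a stratification factor suggests that the sponsor expects it to matter, but does not say how much. This objection stands and limits the point.

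Three other stronger readings fail:

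- *Type I error below 3%.* A simulation that balances within every age-by-severity cell gave 2.8% at an age log odds ratio of 1.5. The protocol balances margins only, and under minimisation the figure is about 3.5%.
- *A narrower interval.* The severity-only standard error is too large only against its own sampling SD. Adding age raises the reported standard error.
- *A biased odds ratio.* The severity-only odds ratio is a different, less conditional quantity. Its being closer to 1 is non-collapsibility, not bias.

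It can also be said that item 4 breaks no uniform rule. Section 13.4 puts an unadjusted Z-test first for the primary endpoint, and item 5 of Section 13.5 uses an unadjusted Wilcoxon test for length of stay and an unadjusted Z-test for ICU admission. That is correct. Still, item 4 is already a covariate-adjusted model that takes one of the two clinical stratification factors and drops the other without a reason.

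Finally, this is a secondary endpoint of a phase 2 trial with no stated power, and the error is on the safe side. That settles the weight of the point, but does not remove it.

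**Conclusion.** The omission is in the text, and nothing elsewhere in the documents repairs it. Its consequence holds only if age is prognostic for the ordinal score. Under the assumptions above, the power loss is about 1 point or less for an age odds ratio up to 2, about 3 points near 3, and about 6 points (5.8 to 6.7 across runs) at 4.5 to 5. Type I error without age falls to about 4% at an odds ratio of 3 and about 3.5% at 4.5 to 5. There is no false-positive inflation. If age has no effect, including it makes no measurable difference (83.2% vs 83.1%).

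The direction is well supported, since simulations with and without site in the minimisation agree. The size is not known from the documents. This is a minor gain in efficiency and consistency, not a flaw that threatens the trial's conclusions.

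**What to change.** In Section 13.5 item 4, specify the proportional odds model for both Day 14 and Day 28 as treatment arm + baseline severity + age group (<65 vs ≥65), with the stratification values as recorded at randomisation. Site is also a minimisation factor and is also absent from this model, so state in the same edit how it is handled.

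The cost is a short text change and one more parameter for 264 patients, with no new data. Make it before unblinding, because adding age afterwards would look like a model chosen on the results.
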